### **6.13.1. Adverse Events**

A listing of AEs occurring either before first dose or after the patient’s last date of study participation will be provided. The listing will include patient identification including the treatment, site number, event information: AE group ID, event start date, Medical Dictionary for Regulatory Activities (MedDRA) System Organ Class (SOC), and Preferred Term (PT), seriousness, severity, outcome, relationship to study drug, time from first dose of study drug to the event, time from last dose of study drug to the event, and time from end of study participation to the event.

A TEAE is defined as an event that first occurred or worsened in severity after baseline. The MedDRA Lowest Level Term (LLT) will be used in the treatment-emergent derivation. The maximum severity for each LLT during the baseline period including ongoing medical history will be used as baseline severity. For events with a missing severity during the baseline period, it will be treated as “mild” in severity for determining treatment-emergence. Events with a missing severity during the postbaseline period will be treated as “severe” and treatment-emergence will be determined by comparing to baseline severity.

The percentages of patients with TEAEs will be summarized by treatment using MedDRA PT nested within SOC. Statistical comparisons will be applied at both the SOC and PT levels. Events will be ordered by decreasing frequency within SOC. For events that are sex-specific, the denominator and computation of the percentage will include only patients from the given sex.

An overview of the number and percentage of patients who experienced a TEAE, serious adverse event (SAE), died due to an AE, discontinued from study treatment or study due to an AE, relationship to study drug, and outcome of the AE will be summarized by treatment.

The percentages of patients with TEAEs, overall and common (common TEAEs occurred in  $\geq 5\%$  of patients before rounding), will be summarized by treatment using MedDRA PT. Events will be ordered by decreasing frequency.

The percentages of patients with TEAEs by maximum severity will be summarized by treatment using MedDRA PT. For each patient and TEAE, the maximum severity for the MedDRA PT is the maximum postbaseline severity observed from all associated LLTs mapping to the MedDRA PT. The maximum severity will be determined based on the non-missing severities. If all severities are missing for the defined postbaseline period of interest, it will show as missing in the table. Only counts and percentages will be included for the TEAEs by maximum severity.

Patient narratives will be provided for all patients who experience any of the following “notable” events:

- death
- serious adverse event
- pregnancy
- permanent discontinuation of study treatment due to AE
- severe adverse events of special interest

#### **6.13.1.1. Deaths**

A listing of all deaths will be provided. The listing will include patient identification including the treatment, site number, date of death, age at the time of enrollment, sex, MedDRA PT of associated AE, time from first dose of study drug to death, time from last dose of study drug to death (if patient had discontinued study drug), investigator reported cause of death, and CEC adjudicated cause of death.

#### **6.13.1.2. Other Serious Adverse Events**

The number and percentage of patients who experienced an SAE (including deaths and SAEs temporally associated or preceding deaths) during the study follow-up will be summarized by treatment using MedDRA PT nested within SOC. Events will be ordered by decreasing frequency within SOC.

A listing of all SAEs will be provided. The listing will include, but not be limited to, treatment, patient identification including the site number, date of event, age at the time of enrollment, sex, MedDRA SOC and PT, severity, action taken, outcome, relationship to study drug, time from first dose of study drug to the event, and event duration.

#### **6.13.1.3. Discontinuation from Study Due to Adverse Event**

The number and percentage of patients who prematurely discontinue the study due to an AE will be summarized by treatment using MedDRA PT nested within SOC. Events will be ordered by decreasing frequency within SOC.

#### **6.13.1.4. Discontinuation from Study Drug Due to Adverse Event**

The number and percentage of patients who prematurely discontinue study drug due to an AE will be summarized by treatment using MedDRA PT nested within SOC. Events will be ordered by decreasing frequency within SOC. Time-to-event analyses will be conducted by treatment on time to study drug discontinuation as well as on time to study drug discontinuation due to an AE.

## 6.13.2. Special Safety Topics

### 6.13.2.1. Hypoglycemic Events

Definitions of different categories of hypoglycemic events are included in [Table GPGH.6.3](#).

**Table GPGH.6.3. Definitions of Hypoglycemic Event Categories**

	Symptoms and/or Signs of Hypoglycemia	Blood Glucose Level
Documented symptomatic hypoglycemia	Yes	≤70 mg/dL (3.9 mmol/L)
Documented asymptomatic hypoglycemia	No	≤70 mg/dL (3.9 mmol/L)
Documented unspecified hypoglycemia	Unknown	≤70 mg/dL (3.9 mmol/L)
Clinically significant documented symptomatic hypoglycemia	Yes	<54 mg/dL (3.0 mmol/L)
Clinically significant documented asymptomatic hypoglycemia	No	<54 mg/dL (3.0 mmol/L)
Clinically significant documented unspecified hypoglycemia	Unknown	<54 mg/dL (3.0 mmol/L)

**Severe hypoglycemia:** Defined as an episode with severe cognitive impairment requiring the assistance of another person to actively administer carbohydrate, glucagon, or other resuscitative actions. Severe hypoglycemia will be reported as an SAE. Severe hypoglycemia will be considered an adverse event of special interest (AESI).

**Nocturnal hypoglycemia:** Defined as any hypoglycemic event that occurs between bedtime and waking.

To avoid duplicate reporting, all consecutive BG values ≤70 mg/dL (3.9 mmol/L) occurring within a 1-hour period may be considered to be a single hypoglycemic event.

Statistical summaries and analyses will exclude hypoglycemic events occurring while on rescue therapy. For each of the aforementioned hypoglycemia categories, incidence as well as rate per patient year of exposure will be provided by treatment. A listing of hypoglycemic events occurring while on rescue therapy will also be provided.

For each of the hypoglycemia categories mentioned above, the incidence of any hypoglycemic event (with blood glucose ≤70 mg/dL [3.9 mmol/L] or <54 mg/dL [3.0mmol/L]) will be analyzed using logistic regression with treatment, country/pooled country, and baseline concomitant oral antihyperglycemic medication as fixed effects and baseline HbA1c and rate of hypoglycemic events at baseline as covariates. The rate of hypoglycemic episodes will be analyzed using a generalized linear mixed-effects model assuming the number of hypoglycemic episodes follows a negative binomial distribution with the mean modeled using country/pooled country, baseline concomitant oral antihyperglycemic medication and treatment as a fixed effects and baseline HbA1c as a covariate. The logarithm of days during the active treatment period will be adjusted as an offset to account for possible unequal treatment duration of follow-up between patients.

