### **Study Procedures**

Patients will perform study procedures listed in the Schedule of Activities (Section 2).

Patients will be permitted to use concomitant medications that they require during the study, except certain medications that may interfere with the assessment of efficacy and safety characteristics of the study treatments. Antihyperglycemic medications other than study drugs are not allowed at any time during the study except as allowed for rescue therapy and/or after early study drug discontinuation. Rescue therapy with other glucose-lowering agents, including prandial insulin, may be medically indicated in certain situations after randomization due to severe, persistent hyperglycemia or early discontinuation of study treatment. Glucagon-like peptide-1 receptor agonists, dipeptidyl peptidase (DPP-4) inhibitors, and pramlintide are prohibited medications and are not allowed as rescue therapies. No other basal insulins are allowed during the course of the study (except for LY3298176 groups).

Patients who develop severe, persistent hyperglycemia based on prespecified thresholds (see Sections 7.2.1.2 and 9.2.2.2) will receive a new glucose-lowering intervention (“rescue therapy”) and will also continue to administer study drug. Patients who need hyperglycemic rescue therapy will continue in the study until they complete all study visits.

Study governance considerations are described in detail in [Appendix 3](#).

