Patients who stop the study drug permanently will receive another glucose-lowering intervention (Section 7.4.2) and will continue participating in the trial according to the protocol to collect all planned efficacy and safety measurements.

Patients discontinuing from the investigational product prematurely for any reason should complete AE and other follow-up procedures per Section 2 Schedule of Activities, Section 9.2 Adverse Event, and Section 9.4 Safety of this protocol.

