**Table GPGH.6.1. Description of Analysis Datasets**

Analysis Set	Description
Screened population	All participants who sign informed consent
Randomized population	All patients who are randomly assigned a treatment arm
modified intention-to-treat (mITT) population	All randomly assigned participants who are exposed to at least 1 dose of study drug. In the event of a treatment error, participants will be analyzed according to the treatment they were randomized.
Efficacy analysis set (EAS)	Data obtained during Study Period II from the mITT population, excluding patients discontinuing study drug due to inadvertent enrollment and data after initiating rescue antihyperglycemic medication or stopping study drug (last dose date +7 days).
Full analysis set (FAS)	All available data obtained during Study Period II from mITT, excluding patients discontinuing study drug due to inadvertent enrollment, regardless of adherence to study drug or initiation of rescue antihyperglycemic medication.
Safety analysis set (SS)	Data obtained during Study Periods II or III from the mITT population, regardless of adherence to study drug or initiation of rescue antihyperglycemic medication.

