### 6.13. Safety Analyses

Unless specified otherwise, safety assessments will be based on the SS ([Table GPGH.6.1](#)). All events that occur between the date of first dose of study drug to the date of patient's safety follow-up visit or patient's end of study participation will be included, regardless of the adherence to study drug or initiation of rescue therapy. For assessing the benefit and risk profile through 52 weeks, selected safety analyses will be conducted by utilizing safety data from first dose through the date of the 52-week visit. Some safety analyses may be conducted after excluding data after the initiation of new antihyperglycemic therapy.

The statistical assessment of homogeneity of the distribution of categorical safety responses among treatment arms will be conducted using Fisher's exact test, unless specified otherwise.

The mean change from baseline differences among treatments at all scheduled visits will be assessed via an MMRM using REML, unless specified otherwise. The model will include country/pooled country, baseline HbA1c ( $\leq 8.5\%$ ,  $> 8.5\%$  [ $\leq 69$ ,  $> 69$  mmol/mol]), baseline concomitant oral antihyperglycemic medication, treatment group, visit and treatment-by-visit

interaction as fixed effects, and baseline value of the safety parameter as a covariate. To model the covariance structure within patients, the unstructured covariance matrix will be used. If this model fails to converge, the covariance structures specified in Section 6.12.1.1 will be tested in order.

For selected safety parameters, time-to-first-event analysis via the cox-proportional hazards model may be conducted. Patients without the event will be censored at the end of study participation. For patients experiencing the event, the “time-to-first-event” will be the time (in days) from first dose to first occurrence of the event.

Where necessary, the rate of events will be analyzed using a generalized linear mixed-effects model assuming the number of events follow a negative binomial distribution and with treatment as a fixed effect. The logarithm of days during the active treatment period will be adjusted as an offset to account for possible unequal treatment duration of follow-up between patients.

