### 6.13.2.2. Severe Persistent Hyperglycemia

A summary of initiation of rescue therapy in response to severe, persistent hyperglycemia will be provided by treatment. If there are a sufficient number of episodes, time-to-first-event analyses for the initiation of rescue therapy will be conducted by treatment using a cox proportional regression model. A listing of patients who initiated rescue therapy will be provided.

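### The hypoglycaemia rate analysis drops events on rescue therapy but says nothing about dropping the days on rescue from its denominators

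*SAP*

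**What the plan says.** Four statements matter.

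- **Events.** For hypoglycaemia, SAP 6.13.2.1 states: "Statistical summaries and analyses will exclude hypoglycemic events occurring while on rescue therapy". Events on rescue are only listed.
- **Denominators.** The same section reports a rate per patient-year of exposure and fits a negative binomial model for which "The logarithm of days during the active treatment period will be adjusted as an offset". SAP 6.13 uses the same offset for event rates in general. Neither section defines the active treatment period, and neither mentions days on rescue.
- **Treatment during rescue.** Under Protocol 5.1 (Study Procedures), patients rescued for severe, persistent hyperglycaemia receive a new intervention "and will also continue to administer study drug". Protocol 9.2.2.2 also describes rescue as add-on to randomised treatment.
- **Default event window.** SAP 6.13.2.1 gives no start or end for counted events, so the SAP 6.13 default applies. Events from first dose to the safety follow-up visit or "end of study participation will be included, regardless of the adherence to study drug or initiation of rescue therapy". The safety analysis set in SAP Table GPGH.6.1 matches this: "Data obtained during Study Periods II or III from the mITT population".

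The nearest defined duration is in SAP 6.10. Duration on study treatment runs from first dose to last dose plus 7 days. It is not linked to the offset, and it does not remove days on rescue.

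**The concern.** A rate needs events and days drawn from the same time. Here a rescued patient's events stop counting when rescue starts, but nothing stops the clock. The later days then add to the denominator and can add nothing to the numerator, which pulls the arm's rate down.

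Hypoglycaemia against titrated insulin is a listed safety comparison (SAP 4.4), and per-arm rates will be reported. Equal rescue time across arms cannot be presumed: Protocol 9.2.2.2 applies the rescue criteria in the degludec group only after Week 16.

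A second, smaller gap works the other way. If the offset covers treatment only while events are counted through safety follow-up, the follow-up events come without person-time.

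**Working it through.** The documents state no hypoglycaemia rate or event count, so there is no plan figure to reproduce.

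**Inputs.** From the documents: a 52-week treatment period and a 4-week follow-up. Assumed: r, the share of an arm on rescue; t, the week rescue starts; rescue continuing to Week 52; a constant event rate. The only related planning figure is a cap of 28% per arm on rescue and premature discontinuation combined (SAP 5.2). It is not a rescue rate.

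**Per-arm rate.** Take Period II days as the denominator, with rescued patients having the arm's average event rate. Countable time is (1−r)×52 + r×t weeks per patient, and counted time is 52 weeks. Reported rate / matched rate = 1 − r(52−t)/52.

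| r | t | r(52−t)/52 | factor |
|---|---|---|---|
| 2% | 24 | 0.02×28/52 = 0.011 | 0.989 |
| 5% | 24 | 0.05×28/52 = 0.027 | 0.973 |
| 10% | 16 | 0.10×36/52 = 0.069 | 0.931 |
| 10% | 24 | 0.10×28/52 = 0.054 | 0.946 |
| 10% | 40 | 0.10×12/52 = 0.023 | 0.977 |
| 28% | 16 | 0.28×36/52 = 0.194 | 0.806 |

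The last row treats the whole planning cap as rescue, so it is an outer bound and not an expectation.

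**Model check.** A negative binomial fit to 200,000 simulated patients (assumed mean 2 events per 52 weeks, dispersion 3, 10% rescued at Week 24) gave 0.949 of the true rate with the 52-week offset. With rescue days removed it gave 1.002.

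**Using the SAP 6.10 duration instead.** If last dose plus 7 days falls at Week 53, 10% rescued at Week 24 gives 0.10×29/53 = 5.5% instead of 5.4%. That definition does not cure the mismatch.

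**Lower event rate in rescued patients.** Let their rate be half that of the others, with r = 10% and t = 24, and set the others' rate to 1.

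- Arm rate with no events excluded: 0.9 + 0.1×0.5 = 0.950.
- As written: (0.9×52 + 0.1×24×0.5)/52 = 48/52 = 0.923, which is 2.8% below 0.950.
- With rescue days removed: 48/49.2 = 0.976, which is 2.7% above 0.950.

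**Rate ratio, from rescue days alone, rescue at Week 24.**

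- 2% against 5% rescued: 0.973/0.989 = 0.984, or 1.017 the other way round.
- 0% against 10% rescued: 0.946, or 1.057 the other way round.
- Same rescue time in both arms: 1.

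**Secondary point, the event window.** Suppose follow-up events count and follow-up days do not.

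- Follow-up rate equal to the on-treatment rate: 56/52 = 1.077, or 56/53 = 1.057 with a 53-week offset.
- Follow-up rate half the on-treatment rate: (52 + 2)/52 = 1.038.

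**The case against.** **The SAP is silent on rescue days; it does not say they are kept.** This stands, and a reader should not infer that the SAP directs their retention. But the exclusion is worded for events only, study drug continues during rescue, and the nearest defined duration contains those days. A programmer following the text would keep them.

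**The protocol already allows for this.** Protocol 10.3.4.1, the hypoglycaemia section, allows analyses that exclude data after another antihyperglycaemic therapy is introduced, and data could include person-time. That sentence is permissive and covers selected analyses. It does not settle the SAP model.

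**Rescued patients may have few hypoglycaemic events, since rescue requires persistent hyperglycaemia.** This stands as to size: the shortfall against the arm's own rate falls from 5.4% to 2.8% in the example above. It also limits the fix, which yields the rate in rescue-free time and not the rate had nobody needed rescue. It does not make events and days match.

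**The follow-up events.** A reader might infer that these will certainly inflate the rates. That rests on a default that applies unless otherwise specified, together with an undefined term. A model built on the active treatment period could reasonably be read as limiting events to that period.

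**The meaning of rescue.** A reader might also infer that it is open whether therapy begun after early discontinuation counts as rescue. One protocol sentence allows rescue "due to severe, persistent hyperglycemia or early discontinuation of study treatment", and Protocol 8.1.1 says: "Patients who stop the study drug permanently will receive another glucose-lowering intervention". The documents as a whole do not support much here. Protocol 5.1 attaches the rescue label to severe, persistent hyperglycaemia. SAP Table GPGH.6.1 separates starting rescue from stopping drug, and SAP 6.13.2.2 summarises "initiation of rescue therapy in response to severe, persistent hyperglycemia". Applying that definition consistently is enough.

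**Conclusion.** The point holds for rescue days. As written, SAP 6.13.2.1 excludes events on rescue without excluding the matching days, from either the patient-years or the offset. The per-arm rate is understated by about r(52−t)/52 if rescued patients have the arm's average rate: 5.4% for 10% rescued at Week 24, 6.9% at Week 16, and less if their rate is lower. All sizes rest on assumed rescue shares and timings.

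A reader might go further and infer that the comparison with degludec is biased. The documents do not establish that. The rate ratio shifts only if rescue time differs between arms, and by about 1.6% for 2% against 5% rescued at Week 24. The logistic incidence analysis has no person-time denominator, and no error-controlled endpoint is involved.

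The undefined active treatment period and the unstated event window need clarifying but are secondary. Severity is minor to moderate.

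**What to change.** In SAP 6.13.2.1, remove days on rescue from both the patient-years of exposure and the offset, so that events and days come from the same eligible time.

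As a secondary clarification, define the active treatment period by its start and end, and apply the same limits to counted events. Events in safety follow-up can then be reported separately, or their days added if they are counted. A short note can state that rescue in this exclusion has the SAP's meaning, based on severe, persistent hyperglycaemia.

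The cost is SAP wording and one derived variable, eligible days per patient. No new data are needed. The downside is slightly less person-time. The text should say that the result is a rate in rescue-free time.

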### 6.13.2.2. Severe Persistent Hyperglycemia

A summary of initiation of rescue therapy in response to severe, persistent hyperglycemia will be provided by treatment. If there are a sufficient number of episodes, time-to-first-event analyses for the initiation of rescue therapy will be conducted by treatment using a cox proportional regression model. A listing of patients who initiated rescue therapy will be provided.

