#### **9.2.2.2. Severe, Persistent Hyperglycemia**

Severe, persistent hyperglycemia will be collected during the trial to assess the risk of extreme imbalance in glycemic control.

Investigators will be trained on the application of criteria for deciding when and how to intervene with patients who do not reach glycemic targets. An additional therapeutic intervention should be considered in patients who develop severe, persistent hyperglycemia after randomization at the discretion of investigator in accordance with American Diabetes Association/European Association for the Study of Diabetes guidance (Inzucchi et al. 2015). Rescue medication will be prescribed as add-on to randomized treatment, and patients will continue to follow the protocol-specified visit schedule.

Add-on glycemic rescue therapy will be allowed for patients who met any one of the following prespecified criteria for severe, persistent hyperglycemia and no intercurrent cause of the hyperglycemia could be identified (investigators should first confirm that the patient is fully

compliant with the assigned therapeutic regimen and that he or she does not have an acute condition causing severe hyperglycemia):

- (a) average daily BG from the once-weekly 4-point SMBG profile  $>270$  mg/dL ( $>15.0$  mmol/L) over at least a consecutive 2-week period any time during the first 8 weeks post randomization;  
OR
- (b) average daily BG from the once-weekly 4-point SMBG profile  $>240$  mg/dL ( $>13.3$  mmol/L) over a consecutive 2-week period at any time 9 to 16 weeks post randomization;  
OR
- (c) average daily BG from the once-weekly 4-point SMBG profile  $>200$  mg/dL ( $>11.1$  mmol/L) over a consecutive 2-week period at any time beyond the first 16 weeks post randomization.  
OR
- (d) HbA1c  $\geq 8.5\%$  at 24 weeks, with inadequate response to the existing regimen defined as improvement in HbA1c over the last 3 months (week 12 to week 24) that is  $<0.3\%$

Rescue therapy option:

For the insulin degludec group, patients can further titrate the insulin degludec. The criteria described above for severe, persistent hyperglycemia will only be applicable after Week 16. The first choice before initiating any rescue therapy for those patients during the initial 16 weeks will be to follow the TTT algorithm to increase the dose of insulin degludec.

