#### 4.4. Safety Objectives

To compare the safety of tirzepatide 5 mg, 10 mg, and 15 mg to insulin degludec for:

[figure not shown]
- treatment-emergent adverse events (TEAEs)
- early discontinuation of study drug due to adverse events (AEs)
- adjudicated pancreatic AEs
- serum calcitonin
- incidence of allergic and hypersensitivity reactions
- incidence of treatment-emergent anti-drug antibodies to tirzepatide
- mean change in systolic and diastolic blood pressure and heart rate from baseline
- occurrence of hypoglycemic episodes
- incidence of initiation of rescue therapy for severe, persistent hyperglycemia

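### Rescue initiation is compared between arms from first dose, although the rescue criteria apply to degludec patients only after Week 16, so differences in eligibility and in glycaemic control are mixed

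*SAP*

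**What the plan says.** SAP 4.4 lists, among the comparisons of each tirzepatide dose with degludec, "incidence of initiation of rescue therapy for severe, persistent hyperglycemia". SAP 6.13.2.2 plans a summary by treatment, a listing and, given a sufficient number of episodes, a Cox model: "time-to-first-event analyses for the initiation of rescue therapy will be conducted by treatment using a cox proportional regression model". SAP 6.13 counts events from the first dose and defines the time scale for patients with an event: "the “time-to-first-event” will be the time (in days) from first dose to first occurrence of the event".

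Protocol 9.2.2.2 sets the criteria. Criterion (a) is a 4-point SMBG average above 270 mg/dL "over at least a consecutive 2-week period any time during the first 8 weeks post randomization". Criterion (b) is an average above 240 mg/dL "over a consecutive 2-week period at any time 9 to 16 weeks post randomization". Criterion (c) is an average above 200 mg/dL beyond Week 16, and criterion (d) is an HbA1c rule at Week 24. A paragraph on the comparator follows. It opens "For the insulin degludec group, patients can further titrate the insulin degludec" and continues: "The criteria described above for severe, persistent hyperglycemia will only be applicable after Week 16". It then says: "The first choice before initiating any rescue therapy for those patients during the initial 16 weeks will be to follow the TTT algorithm".

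No matching deferral is given for tirzepatide. Neither document restricts the rescue comparison to a common window, uses delayed entry, or mentions the unequal applicability.

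**The concern.** The deferral can only concern degludec, because otherwise criteria (a) and (b) would never operate. The same SMBG readings at Week 10 can therefore qualify a tirzepatide patient for rescue, and so for an event, while a degludec patient has the insulin increased and is not an event. The tirzepatide arms have no such deferral even though, by Protocol 7.7.1, escalation to 15 mg takes 20 weeks.

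A by-treatment count from first dose then compares arms that were not subject to the same trigger for the first 16 weeks. A reader of the study report could take a difference in eligibility for a difference in glycaemic control. The two hazards also differ in shape by rule: tirzepatide events can occur throughout Weeks 0-16, while degludec events are deferred and may bunch just after Week 16. One hazard ratio does not describe that well.

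**Working it through.** The documents state no rescue rate, hazard ratio or power for this endpoint, so there is no plan figure to reproduce. The only related number, in SAP 5.2, is a ceiling of 28% for rescue and treatment discontinuation combined. All incidences below are assumptions.

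**Inputs.** Treatment period 52 weeks (Protocol 5.1); degludec deferral to Week 16 (Protocol 9.2.2.2); 355 patients per arm (SAP 5.2).

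**Time under the criteria.** Tirzepatide 52 weeks; degludec 52 − 16 = 36 weeks. 36/52 = 0.69, so 31% of the period is deferred. The ratio is 52/36 = 1.44.

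**Incidence under equal constant hazard, no early degludec rescue and no carry-over.** With h = −ln(1 − p)/52, the degludec arm shows 1 − exp(−36h):

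- p = 2% shows as 1.4%
- p = 3% shows as 2.1%
- p = 5% shows as 3.5%

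**Relaxing the two assumptions that matter.** Let e be the share of risk that falls in Weeks 0-16, and c the share of early degludec cases that are still uncontrolled and are rescued just after Week 16 (carry-over). For low incidence the apparent ratio, tirzepatide to degludec, is about 1/[(1 − e) + e·c]:

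| e | c = 0 | c = 0.5 | c = 1 |
|---|---|---|---|
| 0.10 | 1.11 | 1.05 | 1.00 |
| 16/52 = 0.31 (constant hazard) | 1.44 | 1.18 | 1.00 |
| 0.50 | 2.00 | 1.33 | 1.00 |

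A simulated two-arm Cox analysis (355 per arm, identical true hazards, no degludec rescue before Week 16, 600 runs per setting, incidence 2% to 20%) agrees. Median hazard ratios were 1.39 to 1.50 for constant hazard with c = 0, 1.97 to 2.05 for e = 0.50 with c = 0, and 1.00 to 1.02 whenever c = 1. No setting fell materially below 1.

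**False significance against tirzepatide** (nominal 2.5%), constant hazard: with c = 0, about 6% of runs at 2% incidence, 14% at 5% and 30% at 10%. At 10% incidence it falls to about 9% with c = 0.5 and 3% with c = 1.

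**Would starting the comparison at Week 16 solve it?** Under constant hazard the planned ratio is about 52/(36 + 16c), and a Week 16 landmark gives about 36/(36 + 16c):

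| c | Planned | Landmark |
|---|---|---|
| 0 | 1.44 | 1.00 |
| 0.5 | 52/44 = 1.18 | 36/44 = 0.82 |
| 1 | 1.00 | 36/52 = 0.69 |

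The two are equally far from 1 (as ratios) when (36 + 16c)² = 52 × 36 = 1872, so 36 + 16c = 43.27 and c = 0.45. Above that, the landmark is further from 1, now in favour of tirzepatide, because early tirzepatide cases have left the risk set while carried-over degludec cases are counted.

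**The case against.** The strongest reply is that treat-to-target titration is the degludec regimen. Raising degludec is not a new intervention in the sense of Protocol 5.1, and safety is assessed regardless of rescue. Which randomized regimen needed add-on therapy over 52 weeks is a fair question, and early failures during tirzepatide escalation belong to the answer. This stands, and it is a reason to keep the whole-period summary. It does not remove the problem that the event is triggered under different rules in the two regimens and the SAP does not say so.

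A reader might go further and infer that degludec patients cannot have an event before Week 16, that their hazard is therefore zero, and that the comparison is biased against tirzepatide by a factor of about 1.4. The documents do not support that. The phrase about a first choice before any rescue defers rescue rather than bars it. Protocol 7.2.1.2 says rescue should be considered for degludec patients who meet the criteria, with no Week 16 limit, and Protocol 9.2.2.2 leaves rescue to the investigator's discretion. The thresholds also tighten from 270 to 240 to 200 mg/dL, and criterion (d) arises only at Week 24. This argues against a constant hazard, may leave few events early, and makes carry-over plausible for a degludec patient uncontrolled at Week 15.

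The consequences are limited too. Protocol 10.3.2.3 calls this an exploratory safety endpoint, SAP 6.6 makes no multiplicity adjustment for safety assessments, and the Cox model is conditional on enough episodes. No primary or key secondary conclusion rests on it.

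**Conclusion.** The asymmetry is in the documents and the analysis plan makes no allowance for it. Followed as written, the plan mixes eligibility for the endpoint with glycaemic control. With equal true hazards and no early degludec rescue, any distortion runs against tirzepatide. Its size cannot be derived from the documents: about 1.0 with full carry-over, 1.44 with constant hazard and no carry-over, and about 2.0 if half the risk is early with no carry-over. Any early degludec rescue would shrink it. A fixed ratio of 1.4 is one point in that range, not an estimate. Because the endpoint is exploratory, the severity is minor to moderate.

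**What to change.** In SAP 6.13.2.2:

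- Keep the whole-period summary and label it as a comparison of regimens.
- Report rescue incidence, and the Cox model if fitted, separately for Weeks 0-16 and after Week 16, noting that the criteria did not apply equally in Weeks 0-16.
- Do not make a Week 16 landmark the sole comparison. Wherever a post-Week 16 result is shown, state that it conditions on being unrescued at Week 16 and may count carried-over degludec cases.
- As a supplement, compare the proportion in each arm whose SMBG data meet the same thresholds in the same weeks, whether or not rescue was started. This uses diary profiles that patients are already asked to keep. The weekly profile is encouraged rather than required (Protocol Section 2), so report its completeness by arm.

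Separately, Protocol 9.2.2.2 and 7.2.1.2 should be reconciled on whether degludec patients can be rescued before Week 16. No clinical rule is proposed here.

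The cost is SAP wording, a few extra tables and fewer events in each period.
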